# 7 ASSESSMENT OF SAFETY

# 7.1 Specification of Safety Parameters

#### 7.1.1 **Primary Endpoint**

The primary objective of this study is to evaluate the safety of rAAV2tYF-CB-hRS1 administered by intravitreal injection in patients with XLRS. The primary safety parameter will be the frequency of Grade 3 or 4 local (ocular) or systemic AEs that occur during the 12 months after study agent administration.

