3.1 Primary Variable

The primary variables are the:

- Number and proportion of participants experiencing ocular or non-ocular adverse events (AEs),
- Number and proportion of participants experiencing any clinically significant abnormal hematology or chemistry parameter

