Individuals who have participated in the natural history study XLRS-001, entitled "Clinical Evaluation of Individuals with XLRS", may have discontinued their participation in that study and enrolled in this study if all appropriate entry criteria were met. In this case, results of the evaluations from the most recent visit in the natural history study could be used as part of the appropriate screening visit evaluations for this study, as long as all the evaluations were conducted according to the Study Manual of Procedures and Reading Center Manual of Procedures of this study, and the visit occurred no more than 3 months prior to the planned date of study agent administration. If the most recent visit examinations are performed.

Enrollment began with Group 1A and will proceed to subsequent groups after review of safety data by a Data and Safety Monitoring Committee (DSMC). After review of safety data from Group 1A, participants will be enrolled in Groups 1B and 2 concurrently. After review of safety data from Groups 1A, 1B and 2, participants will be enrolled in Group 3. After review of safety data from Groups 1A, 1B, 2, and 3, participants \geq 18 years of age will be enrolled in Group 4. As ocular inflammation has been seen in the first 12 subjects enrolled in the study and pediatric participants might be more prone to inflammation, pediatric participants (age 6-17) in this study will first be treated at the middle dose (Group 2A) prior to the enrollment in Group 4.

Within groups 1A, 2, 2A and 3, enrollment of participants will be staggered by at least 2 weeks to allow adequate time for review of safety information by the investigators and sponsor.

Within group 4, enrollment of the first 3 pediatric participants will be staggered by at least 2 weeks to allow adequate time for review of safety information by the investigators and sponsor.

Approximately 27 participants are to be enrolled in this study. Enrollment in this study is anticipated to take approximately 30 months. Enrolled participants will have frequent follow-up visits during the first year after study agent administration.

To monitor for delayed AEs and assess the duration of any changes in visual function or structure that occur, participants are followed annually for an additional 4 years after the Month 12 visit.

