14.1 Adverse Events

An AE is defined as any untoward medical occurrence associated with the use of a drug in humans, whether or not the event is considered drug-related. An AE can therefore be any unfavorable and unintended sign (e.g., an abnormal laboratory finding), symptom, or disease occurring after the first dose of study drug, without any judgment about causality. Any pre-existing medical condition that worsens after first administration of the study drug will also be considered a new AE. The occurrence of an AE may come to the attention of study personnel during study visits and interviews or by a study recipient presenting for medical care. All AEs must be graded for intensity and relationship to study product.

Every AE recorded in this study must be assessed by the investigator to determine whether or not it meets the definition of a dose-limiting toxicity (DLT). A DLT is defined as any toxicity determined by the investigator to be related to the study agent and deemed serious or sufficiently severe to preclude dose escalation. For the purpose of this study, any grade 4 or 5 event (per the Common Terminology Criteria for Adverse Events [CTCAE] v4.0 criteria) that is assessed as possibly, probably or definitely related to the study drug will be considered to be a DLT.

Treatment-emergent adverse events (TEAE) are defined as any event that occurs or worsens on or after the day that study treatment is administered. AEs which began prior to treatment will not be included in the summary tables but will be included in the AE data listings.

An overall summary will be presented that includes the number of TEAEs and the number and percentage of subjects who experienced at least one TEAE, by group. This summary will also include breakdowns of TEAEs further categorized as ocular (study eye, fellow eye, and both eyes separately) or non-ocular, Grade 3 or 4 local (ocular) or systemic AEs that occur during the 12 months after study agent administration, serious TEAEs (SAEs), TEAEs by maximum severity, TEAEs by maximum relationship to study agent, TEAEs by relationship to study agent injection procedure, and TEAEs leading to subject withdrawal.

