14.5 Slit-Lamp Biomicroscopy Examination

A dilated slit-lamp examination will be performed using the investigator's standard procedure. Documentation will include the presence or absence of central and peripheral schisis.

08 August 2017

A slit-lamp biomicroscopy examination of the cornea, conjunctiva, anterior chamber, iris, lens, and vitreous will be performed at each visit.

Shifts from baseline to worst value during follow-up will be tabulated. A subject listing of the slit-lamp biomicroscopy parameters will also be produced.

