15.9 Fundus Photography

Fundus photography will be performed at the baseline visit and at the visit 12 months after study agent administration.

The results will be summarized using counts and percentages for each group and for all subjects at each visit for each eye. Percentages will be based on the number of subjects with responses. Fundus

08 August 2017

photography parameters include Any evidence of increased inflammation, Hemorrhage, Retinal detachment, Is there RPE disturbance or atrophy in the fovea, Any changes from baseline visit. A subject listing of the fundus photograph parameters will also be produced.

16. Long-term Follow-Up (LTFU)

After the completion of 9 study visits over the course of one year after study agent administration, longterm follow-up (LTFU) will be conducted annually for an additional 4 years after the Month 12 visit. In accordance with regulatory guidance for gene therapy clinical trials, information will be obtained about any cancer, neurological, autoimmune or hematological disorder that developed or worsened since the last visit. A subject listing containing this information will be provided.

17. Interim Analysis

No interim analysis will be conducted for this study. Preliminary analyses of available data may be conducted during the study.

18. Data and Safety Monitoring Committee

Refer to section 4.1.

19. Changes from Protocol-Stated Analyses

- Change over time in titers of serum antibodies and IFN-γ ELISPOT responses to retinoschisin (RS1) is moved from secondary safety outcomes to other outcomes.
- Inferential statistics for all efficacy endpoints will be calculated.
- Visual field parameter (square root of the loss variance) will not be read by the Reading Center.

20. References

¹ Hood DC and Birch DB. A computational model of the amplitude and implicit time of the b-wave of the human ERG. Vis Neurosci 1992;8:107-26

² Patel PJ, Chen FK, Da Cruz L, Rubin GS, and Tufail A. *Test-retest variability of reading performance metrics using MNREAD in patients with age-related macular degeneration*. Invest Ophthalmol Vis Sci 2011;52:3854-9

21. Revision History

Documentation of revision to the SAP will commence after approval of the Final version 1.0.

22. Tables

Table Number	Title
Table 14.1.1	Subject Disposition
Table 14.1.2	Demographics

Table 14.1.3	Vital Signs
Table 14.1.4	Medical History
Table 14.1.5	Concomitant Medications
Table 14.2.1.1	Best Corrected Visual Acuity

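### Most adverse event tables have no observation window, data-cut rule or person-time, so at any analysis before Year 5 group counts and percentages are mixed up with length of follow-up

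*SAP*

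**What the plan says.** **Events.** SAP 14.1 sets a start and no end: "Treatment-emergent adverse events (TEAE) are defined as any event that occurs or worsens on or after the day that study treatment is administered". The overall summary reports "the number of TEAEs and the number and percentage of subjects who experienced at least one TEAE, by group", and the tables by system organ class and preferred term count subjects in the same crude way. One category has a window: "Grade 3 or 4 local (ocular) or systemic AEs that occur during the 12 months after study agent administration". It is a line in the overall summary and has its own Table 14.3.4. It corresponds to Protocol 7.1.1: "The primary safety parameter will be the frequency of Grade 3 or 4 local (ocular) or systemic AEs that occur during the 12 months". SAP 3.1 does not carry that window over. Its first primary variable is the count and proportion of participants with any AE, ocular or not, without a time limit.

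**Eye examinations.** For the slit lamp, SAP 14.5 says: "Shifts from baseline to worst value during follow-up will be tabulated". SAP 14.7 applies the same rule to indirect ophthalmoscopy.

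**Follow-up.** The visit schedules in both documents continue AE review at Years 2 to 5. SAP 13.1 plans only a listing of agent administration. Neither document plans a summary of follow-up time or an event rate per participant-year.

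**Timing.** SAP 4.1 states: "Enrollment in this study is anticipated to take approximately 30 months". Groups open in sequence after safety reviews. Protocol 14.4 places the review of all safety and efficacy data at the end of the study. SAP 17 plans no interim analysis but adds: "Preliminary analyses of available data may be conducted during the study". It gives no rule for the data cut. The version 8.0 entry in Protocol Appendix C refers to a 12-month analysis and a favourable safety conclusion from it.

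**The concern.** Safety is the primary objective, and no inferential comparison among groups is planned (Protocol 10.7). Readers will therefore judge safety by group from descriptive tables and listings. A crude proportion with at least one event rises with time observed. Groups entered at different dates, so tables run as written at an early cut give longer observation to the groups that entered earlier. A difference between groups could then reflect calendar time rather than dose or age.

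One comparison is plainly exposed. SAP 4.1 says children might be more prone to inflammation, and Group 2A receives the same dose as the adult Group 2. Group 2 entered early and Group 2A late, so at an early cut the children would have been watched for less time. SAP 9.4 also pools the two as 2+2A.

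The intensity of observation changes too: nine post-dose visits in the first year, then one a year (Protocol 6.15).

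**Working it through.** **1. The plan's own figures.** The only numerical design figures are confidence limits for dose-limiting toxicity with no events (Protocol 10.5, SAP 6). The exact two-sided upper limit is 1 − 0.025^(1/n). For n = 9 it is 33.63% and for n = 27 it is 12.77%. Both reproduce. They do not bear on follow-up, and the documents give no AE rates.

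**2. Follow-up at a data cut.** Inputs are accrual of about 30 months (SAP 4.1) and planned follow-up of 12 + 4 × 12 = 60 months for every participant (SAP 4.1). At t months after the last dosing, the first participant has min(60, 30 + t) months and the last has min(60, t).

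| Last participant reaches | First (months) | Last (months) | Ratio |
|---|---|---|---|
| Month 12 | 42 | 12 | 3.5 |
| Year 2 | 54 | 24 | 2.25 |
| Year 3 | 60 | 36 | 1.67 |
| Year 5 | 60 | 60 | 1.0 |

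**3. Effect with a constant event rate (assumed), same rate for both participants, at the Month 12 cut.** P(at least one event) = 1 − exp(−rate × years), with 42/12 = 3.5 years against 1 year.

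| Rate per year | First, no window | Last, no window | Both, 12-month window |
|---|---|---|---|
| 0.1 | 29.5% | 9.5% | 9.5% |
| 0.5 | 82.6% | 39.3% | 39.3% |
| 1 | 97.0% | 63.2% | 63.2% |
| 2 | 99.9% | 86.5% | 86.5% |

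Expected event counts are rate × years, so they differ 3.5-fold at every rate (for example 1.75 against 0.50 at 0.5 per year).

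**4. Effect if most events come early.** Suppose a share p of participants has an event soon after injection and a constant rate applies as well. Then P = 1 − (1 − p) × exp(−rate × years). First against last participant at the Month 12 cut:

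| p | 0.1/yr | 0.5/yr | 1/yr |
|---|---|---|---|
| 50% | 64.8% v 54.8% | 91.3% v 69.7% | 98.5% v 81.6% |
| 80% | 85.9% v 81.9% | 96.5% v 87.9% | 99.4% v 92.6% |
| 95% | 96.5% v 95.5% | 99.1% v 97.0% | 99.8% v 98.2% |

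The gap is about 4 to 9 points at p = 80% and 1 to 2 points at p = 95%. A category with few early events, such as an SAE or a single preferred term, behaves more like step 3.

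**5. Does follow-up track dose?** Not consistently. Groups 1B (lower dose) and 2 (middle dose) enrol together. Group 2A (middle dose) was introduced after the first 12 subjects, which matches 1A + 1B + 2 + 3 = 3 + 3 + 3 + 3. Protocol 5.6 also puts the Group 3 review third and the Group 2A review fourth. Group 3, at the higher dose, therefore has longer follow-up than Group 2A. Group 4 receives a maximum tolerated dose that the documents do not fix.

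**6. Limit of a 12-month window.** It equalises follow-up only once everyone has reached Month 12. If the last participant is at Month 3, windowed follow-up is 12 against 3 months, and at 0.5 per year the proportions are 39.3% against 11.8%.

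**The case against.** The strongest reply is that planned follow-up is the same 60 months in every group, that Protocol 14.4 reviews all data at study end, and that SAP 17 plans no interim analysis. This stands for the final analysis. A reader might infer that lower-dose groups will show more events in the final tables merely because they enrolled earlier. The documents do not support that: the ratio is 1.0 at Year 5, and only unequal withdrawal could separate the groups. Step 5 also rules out a general claim that follow-up falls as dose rises.

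The size is easily overstated as well. The 42 against 12 months compares two participants, not two groups. No dosing dates by group are given, and group means must differ by less. Constant rates are also doubtful, because inflammation in the primate study was maximal at 4 weeks and then improved (Protocol 1.2.2). Step 4 allows for this.

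Much is already protected. The protocol's primary safety parameter keeps its 12-month window. Escalation rests on DSMC reviews after the Week 2 visit and on dose-limiting toxicity. AE onset dates are collected and all AEs are listed. Cumulative tables also suit a study meant to detect delayed events.

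What remains is the early cut. SAP 17 permits one without a cut rule, and Appendix C shows that a 12-month analysis supported a safety statement. Appendix C does not say which AE window was used, so it is not evidence that follow-up was in fact unequal. It shows that a conclusion was drawn before Year 5 under a plan that fixed no window for most AE tables.

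**Conclusion.** The point holds for any analysis before all participants complete Year 5. Except for the Grade 3-4 summary, the event tables and worst-value shift tables as written would confound group differences with follow-up time. The extreme contrast is 3.5-fold, first against last participant, when the last reaches Month 12. It assumes that accrual takes the full 30 months. Differences between groups are smaller and may run either way with dose.

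The any-AE proportion may move by only a few points if most participants have an early event. Raw event counts, SAEs and individual preferred terms could move much more: 29.5% against 9.5% for the same two participants at an assumed 0.1 per year. All event rates here are assumptions.

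Two further inferences go too far. One is that a true dose gradient would be hidden or reversed; that depends on the assumed rates and on the first-against-last contrast. The other is that Year 5 proportions must saturate. At 1 and 2 per year they reach 99.3% and almost 100%, but at 0.3 and 0.6 per year they are 1 − exp(−1.5) = 78% and 1 − exp(−3.0) = 95%, still well apart.

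This is a worthwhile, inexpensive improvement, not a flaw in the planned end-of-study analysis.

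**What to change.** - In SAP 14.1, add a Day 0 to Month 12 version of Tables 14.3.1 to 14.3.3 and 14.3.5 to 14.3.13, and name it as the basis for comparing groups. It matches the window already used in Table 14.3.4. Apply the same window to the any-AE variable in SAP 3.1.
- In SAP 14.5 and 14.7, add the same window to shift Tables 14.4.5 and 14.4.7.
- Keep the cumulative tables, or show events with onset after Month 12 separately, with participant-years and events per participant-year by group.
- In SAP 17, state the data cut-off for any analysis before Year 5 and report follow-up time by group. If some participants have not reached Month 12, or have withdrawn, the participant-years are needed for the first-year tables too.

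The cost is SAP wording and a second run of the same tables. No new data are needed, since AE onset dates are already collected (Protocol 7.3.1).

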### 5.7 Prior and Concomitant Therapy

To reduce the risk of intraocular inflammation, participants may be placed on prophylactic steroids prior to the study agent administration as described in the Study Manual of Procedures.

Potential participants who are taking a carbonic anhydrase inhibitor can be recruited for enrollment in this study but they will be required to discontinue this treatment at least 3 months prior to receiving study agent in order to meet the eligibility criteria.

Participants in all groups will be advised not to take any carbonic anhydrase inhibitor medication during the 6 months after study agent administration. At the Month 6 visit, the investigator may discuss potential use of carbonic anhydrase inhibitor with the subject. Short term carbonic anhydrase inhibitor use to treat IOP spikes after intravitreal study agent administration is allowed.

Participants will be instructed to discontinue aspirin, aspirin-containing products, and any other drugs that may alter coagulation, at least 7 days prior to study agent administration. Participants will be told they may resume taking these types of products starting the day after study agent administration.

Elevated intraocular pressure will be treated using standard methods at the discretion of the investigator.

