#### 7.2.1 Adverse Events and Serious Adverse Events

#### 7.2.1.1 Definition of an Adverse Event

The International Conference on Harmonisation (ICH) E6 Good Clinical Practice (GCP) guidelines define an AE as "any untoward medical occurrence in a patient or clinical investigation subject administered a pharmaceutical product and which does not necessarily have a causal relationship with this treatment." An AE can therefore be any unfavorable and unintended sign (including an abnormal laboratory finding), symptom, or disease temporally associated with the use of a medicinal (investigational) product. The occurrence of an AE may come to the attention of study personnel during study visits and interviews or by a study recipient presenting for medical care. All AEs must be graded for intensity and relationship to study product.

An AE **does** include:

- Exacerbation of a pre-existing illness,
- An increase in frequency or intensity of a pre-existing episodic event or condition,
- A condition detected or diagnosed after study agent administration even though it may have been present prior to the start of the study,
- Continuous persistent disease or symptoms present at baseline that worsen following the start of the study.

An AE does not include:

- A medical or surgical procedure (e.g., surgery, endoscopy, tooth extraction, transfusion); the condition that leads to the procedure may be an AE,
- A pre-existing disease or conditions present or detected at the start of the study that does not worsen,
- Situations where an untoward medical occurrence has not occurred (e.g., normal pregnancy, hospitalizations for cosmetic elective surgery, social and/or convenience admissions),
- Overdose of either study agent or concurrent medication without any signs or symptoms.

AEs may include pre- or post-treatment events that occur as a result of protocol-mandated procedures (e.g., invasive procedures, modification of subject's previous therapeutic regimen). Intercurrent illnesses that occur after screening but before starting treatment, and that are not the result of protocol-mandated procedures, do not need to be captured as AEs.

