#### 7.2.1.2 Intensity of an Adverse Event

All AEs will be assessed by the investigator using the following guidelines to quantify intensity:

- Mild: Events that do not interfere with daily activities and require no medical intervention.
- Moderate: Events that cause some interference with daily activities and may require simple medical interventions.
- Severe: Events that prevent usual daily activities and require medical intervention.
- Life-threatening: Any adverse drug experience that places the subject, in the view of the investigator, at immediate risk of death from the reaction as it occurred, i.e., it does not include a reaction that had it occurred in a more severe form, might have caused death.
- Fatal: Any AE that causes the death of the subject. Except for sudden and unexpected death, death is not an AE, but rather the event that caused the subject to die is the AE.

Changes in the intensity of an AE should be documented to allow an assessment of the duration of the event at each level of intensity to be performed. AEs characterized as intermittent require documentation of onset and duration of each episode.

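### SAP 14.1 counts worsening after injection as treatment-emergent, then keeps every AE with an earlier start out of the summary tables, so a narrow class of true TEAEs can be lost

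*SAP*

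**What the plan says.** Three statements in SAP 14.1 bear on the point.

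- The definition of treatment-emergent: "Treatment-emergent adverse events (TEAE) are defined as any event that occurs or worsens on or after the day that study treatment is administered".
- The table rule, in the next sentence: "AEs which began prior to treatment will not be included in the summary tables but will be included in the AE data listings".
- Earlier in the section: "Any pre-existing medical condition that worsens after first administration of the study drug will also be considered a new AE".

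The protocol supplies the background.

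- Section 7.3.1 treats a condition present at screening as pre-existing and has it recorded as an AE if it deteriorates. It also lists date of onset among the items collected.
- Section 7.2.1.1 allows some events before dosing to be AEs: "AEs may include pre- or post-treatment events that occur as a result of protocol-mandated procedures". Other illness arising between screening and treatment need not be captured.
- Section 7.2.1.2 deals with change within one event: "Changes in the intensity of an AE should be documented to allow an assessment of the duration of the event". The duration is wanted separately for each intensity level.
- Under Section 5.7, "participants may be placed on prophylactic steroids prior to the study agent administration". Appendix A ticks this prophylaxis, and AE review, at the baseline visit, which falls within 7 days before dosing. Screening falls within 3 months before dosing.
- Section 10.7.2 tabulates adverse experiences at maximum intensity and has no exclusion by start date.

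**The concern.** A programmer needs one rule for which AE records enter the TEAE tables, and SAP 14.1 gives two. The definition admits an event that started before treatment if it worsens afterwards. The table rule looks only at when the event began. Where they differ, the table rule removes events and never adds any, so a literal reading can only make the tables look safer.

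Safety is the primary objective. SAP 3.1 makes the number and proportion of participants with ocular or non-ocular AEs a primary variable, and the dose-escalation groups are small. SAP Section 19, which lists departures from the protocol's analyses, does not mention the start-date exclusion.

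**Working it through.** **Which events are in dispute.** Each kind of event is put through both rules.

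| Event | TEAE definition | Table rule, read literally | Agree? |
|---|---|---|---|
| Starts after injection | in | in | yes |
| Condition present at screening, worsens after injection, recorded as a new AE | in | in (the new AE starts after dosing) | yes |
| AE first recorded between screening and injection, worsens afterwards, given a new record | in | in | yes |
| AE first recorded between screening and injection, worsens afterwards, no new record | in | out | **no** |
| Starts on Day 0 before the injection | in (the definition works by day) | out (it began before treatment) | **no** |
| Starts before Day 0, does not worsen | out | out | yes |

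Two rows conflict. The fourth depends on how worsening is recorded, which neither document settles. Protocol 7.2.1.2 asks for intensity changes to be documented, but does not say whether a worsened AE stays on one record with its first start date or gets a new one. In the fifth row, anesthetic and, at the investigator's discretion, an anterior chamber tap come before the injection (Protocol 5.4). The SAP's general AE definition adds a third version, because it refers to "disease occurring after the first dose of study drug, without any judgment about causality".

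**Direction.** The literal table set is the TEAE set minus the two conflicting rows. A subset cannot have a larger count, so the error runs one way.

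**The plan's own safety figures.** Protocol 10.5 and SAP Section 6 give 95% intervals for a dose-limiting toxicity rate with no events. The exact two-sided (Clopper-Pearson) upper limit for 0 of n is 1 − 0.025^(1/n):

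- n = 9: 1 − 0.025^(1/9) = 33.63%, as stated.
- n = 27: 1 − 0.025^(1/27) = 12.77%, as stated.

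These figures are correct and do not change. The same method is used below.

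**Size of one misclassification.** Inputs are groups of 3 (1A, 1B, 2 and 3), a group of up to 6 (2A), and the stated total of about 27. Assume one participant whose only qualifying AE falls in a conflicting row. The proportion shifts by 1/n.

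| n | Table rule: proportion (95% CI) | TEAE definition: proportion (95% CI) | Shift in points |
|---|---|---|---|
| 3 | 0/3 = 0% (0 to 70.76) | 1/3 = 33.3% (0.84 to 90.57) | 33.3 |
| 6 | 0/6 = 0% (0 to 45.93) | 1/6 = 16.7% (0.42 to 64.12) | 16.7 |
| 27 | 0/27 = 0% (0 to 12.77) | 1/27 = 3.7% (0.09 to 18.97) | 3.7 |

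This is the effect of a single case, not an estimate of how often it happens.

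**The case against.** The case on the other side is that the section, read as a whole, already handles worsening. A worsened pre-existing condition is a new AE, the TEAE definition includes worsening, and the natural sense of the table rule is that AEs which are not treatment-emergent are only listed. The affected pool is also small. Conditions present at screening are outside it, and most illness arising before dosing need not be recorded. What remains is mainly AEs caused by study procedures or prophylaxis, and prophylaxis is optional. Nothing is hidden either: all AEs go into a by-subject listing, and SAEs and DLTs have their own.

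Most of this stands, and it limits the point. It does not reconcile the two sentences. The new-AE clause speaks of a pre-existing medical condition, which Protocol 7.3.1 ties to presence at screening. It could be stretched to any AE open at dosing, but the SAP does not say so. The clause also does nothing for events on Day 0 before the injection. Listings show individual cases but do not correct a count in a table.

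A reader might infer two stronger things that the documents do not support.

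- *Worsened events in general drop out of the primary safety counts.* They do not. Worsening of a condition present at screening is recorded as an AE, and it is not established that a later AE keeps its early start date when it worsens.
- *Steroid-related events before Day 0 are wrongly left out, so the risk of prophylaxis plus injection is understated.* If such an event does not worsen, both sentences leave it out, which is the usual treatment-emergent convention. The stated objective is the safety of the study agent, and the protocol's primary safety parameter (Section 7.1.1) counts Grade 3 or 4 AEs in the 12 months after administration. A separate row for these events is optional.

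**Conclusion.** The contradiction in SAP 14.1 is real, narrow and one-directional. Read literally, the table rule removes two classes of event that the SAP itself defines as treatment-emergent: AEs first recorded between screening and injection that worsen afterwards without a new record, and events that start on Day 0 before the injection.

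The total effect cannot be computed, because the documents give no count of such events. Per participant it is 33.3, 16.7 or 3.7 points for n = 3, 6 or 27. That rests on two assumptions: the table rule is applied as written, and the participant has no other AE that qualifies for the same row. The second assumption is more likely to hold in rows for single preferred terms or for Grade 3 or 4 events than in the any-AE row, since Protocol Section 3 reports ocular inflammation among the first 12 subjects. If worsening always opens a new record dated after dosing, only the Day 0 events remain in dispute.

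**What to change.** Replace the table rule in SAP 14.1 with: *AEs that began before the day of treatment and did not worsen on or after that day will be listed only; AEs that worsen on or after that day, and AEs that start on that day, are counted as TEAEs, at their maximum intensity on or after that day.*

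Three short additions would help:

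- State whether a worsened AE gets a new record and start date.
- Make the SAP 3.1 primary variable say whether it means all AEs or TEAEs.
- Record the start-date rule in SAP Section 19.

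The cost is a few sentences and one change to the record-selection rule. No sample size or stated interval changes. Protocol Appendix C refers to a 12-month analysis, so for tables already produced, the AE listing should be searched for start dates before or on Day 0, with later worsening checked for the earlier ones. In a study of about 27 participants that is a small task. Some counts may rise slightly.
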